Sample: The key outcome measure we will use is the overall system usability scale (SUS) score (described below). Given a standard deviation for SUS of 10 units (scale is 0-100 with SUS<50 being poor and SUS>80 being very good) we want the signal to be clear when the difference recorded is 20 units distinguishing between poor and good usability. When there are at least 10 participants per group such a difference can be achieved with 98.8% power for a single comparison. Multiple comparisons however will be made, and the power drops to 97.2% for two comparisons, but remains more than 90% for up to seven comparisons. This allows a sufficient number of comparisons to be meaningfully made in our context. In order to assess the comprehensibility, usability, and acceptability of the QualDash prototypes to all the intended categories of user and to gain a patient and carer perspective, a purposive sample of members of the cardiology and PICU clinical teams, the quality sub-committee, and the Trust board, local commissioners, and members of our LAG will be invited to participate, with a minimum of 10 participants per group.

Data collection: A controlled user experiment will be run, using a mixed factorial experimental design, with technology (current presentation of NCA data and two QualDash prototypes) and task as within-participant variables and role, NCA (MINAP or PICANet), and graph literacy (high or low) as between-participant variables.

Prior to the experiment, participants will be asked to complete an online demographic questionnaire, which will include Galesic and Garcio-Retamero's scale for measuring graph literacy. This scale, developed specifically for the health domain, measures both basic and advanced graph reading skills and comprehension across different types of graphs. The scale consists of 13 items and measures three levels of graph comprehension: i) the ability to read the data; ii) the ability to read between the data (to find relationships in the data); and iii) the ability to read beyond the data (e.g. to be able to predict a future trend from a line chart). Participants will be categorised as high or low literacy, using the median split of a high literacy score of nine or more correct responses, and then stratified prior to randomisation into an experimental group (high vs low literacy).

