Each participant will complete a series of tasks in each condition. Details of the QualDash prototypes to be evaluated and tasks to be undertaken will be dependent on the outputs of Phase 1 and the Phase 2 focus groups. The order of technology used and the task order will be determined by a computer randomisation program. On completing each task, participants will be asked to record their decision, certainty and, using the NASA task load index, 92 their mental workload.

Time to complete each task will be recorded. Morae software will be used for recording participants' interaction with the QualDash prototypes, enabling capture of audio, video, on-screen activity, keyboard and mouse input.

To assess usability and acceptability of the QualDash prototypes, following completion of tasks on each prototype participants will be asked to complete the system usability scale (SUS), a flexible questionnaire designed to assess any technology.⁹³ The SUS is quick and easy to complete, consisting of 10 statements that are scored on a 5-point scale of strength of agreement, with final scores ranging from 0-100. On completion of tasks in all conditions, we will carry out semi-structured interviews with participants to explore their views of the two QualDash prototypes in more detail.

Analysis: Quantitative data (time to complete task, accuracy, certainty, perceived workload, and SUS score) will be analysed using analyses of variance (ANOVA). Qualitative data (from the Morae recordings and interviews) will be analysed using the methods previously described.

The analysis will be used to: make further refinements to the QualDash program theory, adding details regarding the impact of an individual's graph literacy as a contextual factor; determine which QualDash prototype should be used in the evaluation; determine if further revisions to the QualDash prototype are required before the evaluation and what they should be.

Outputs

- An interactive web-based quality dashboard for clinical teams, quality sub-committees, boards, and commissioners, using novel visualisation techniques and tailored to meet the needs of different users, that can be adapted for all NCAs, the design based on existing theory and significant engagement with suppliers and users of NCA data; and
- A technical specification for QualDash.

Phase 3: QualDash implementation *Objective*

• To use the program theory to co-design an implementation strategy for QualDash (Objective 3).

Summary of method

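### The controlled user experiment analyses a 13-item graph literacy score only as high or low; keeping the score would give a more precise answer on literacy at almost no cost

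*Protocol*

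**What the plan says.** All of this is in Protocol section 2c, Controlled user experiment. Under Data collection, a graph literacy scale is given before the experiment: "The scale consists of 13 items and measures three levels of graph comprehension". Participants are sorted into two classes "using the median split of a high literacy score of nine or more correct responses", and the same two classes are used to stratify before randomisation. The design is mixed factorial. Technology (current presentation and two prototypes) and task vary within participant, with "role, NCA (MINAP or PICANet), and graph literacy (high or low) as between-participant variables".

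Under Analysis, time, accuracy, certainty, workload and SUS score go into analyses of variance, and no continuous literacy term is mentioned. The results are to refine the program theory, "adding details regarding the impact of an individual's graph literacy as a contextual factor", as well as to choose a prototype and decide on revisions. The Background (Dashboards) supplies the motive: it cites a study in which people with low graph literacy understood numbers better, while those with high literacy understood graphs better.

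**The concern.** A score with 14 possible values (0 to 13) is collected and then analysed with two. Someone with nine correct is treated as identical to someone with 13, and as different in kind from someone with eight. If the outcome changes gradually with literacy, that lowers the precision of the estimated literacy effect.

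The question suggested by the Background is whether literacy changes the benefit of one presentation over another, which is a literacy-by-technology interaction. The Protocol's sample size argument does not address it. Avoidable loss of precision therefore falls on a question with no planned power. The Protocol fixes the form of the variable itself, so this is not a detail left open for a statistical analysis plan.

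**Working it through.** **1. The plan's own figures.** The only power figures in section 2c concern SUS: "Given a standard deviation for SUS of 10 units", a difference of 20 and 10 participants per group. The standardised difference is 20/10 = 2, the noncentrality is 2 × √(10/2) = 4.47, and there are 18 degrees of freedom. Alpha and sidedness are not stated, so I assume two-sided 0.05, divided by the number of comparisons k.

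| k | Computed | Stated |
|---|---|---|
| 1 | 98.8% | 98.8% |
| 2 | 97.2% | 97.2% |
| 7 | 90.7% | more than 90% |

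The figures reproduce. None of them involves the literacy factor.

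**2. Information kept by a two-level split, normal score.** With a linear effect, the share of information kept is the squared correlation between the score and its high/low indicator:

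r² = φ(z)² / [p(1 − p)],

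where p is the share in one class, z is the matching normal quantile and φ is the normal density. The required sample size grows by about 1/r². The same ratio applies to the interaction, because each participant's difference between two technologies can be regressed on literacy in the same way.

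| Split | Calculation | Kept | Lost | 1/r² |
|---|---|---|---|---|
| 50:50 | 0.3989² / 0.25 | 64% | 36% | 1.57 |
| 70:30 | 0.3477² / 0.21 | 58% | 42% | 1.74 |
| 80:20 | 0.2800² / 0.16 | 49% | 51% | 2.04 |
| 90:10 | 0.1755² / 0.09 | 34% | 66% | 2.92 |

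The Protocol gives no score distribution, so the unequal splits are assumptions.

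**3. The actual 0-13 scale cut at nine.** I used a normal distribution rounded to whole scores, with an assumed SD of 1.5 to 2.5.

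| Underlying mean | Information lost |
|---|---|
| 8.5 (half score high) | 33.7% to 34.3% |
| 9 | 33.4% to 36.3% |
| 10 | 37% to 53% |
| 11 | 44% to 75% |

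The smallest loss found was 33.4%, hence at most about two thirds kept for a bell-shaped score.

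**4. Where the loss is smaller.** For a flat score over 0 to 13, the total variance is (14² − 1)/12 = 16.25. The high class (9 to 13) has mean 11 and the low class (0 to 8) has mean 4. The between-class variance is (5/14)(9/14)(11 − 4)² = 11.25, so 11.25/16.25 = 69% is kept and 31% lost. If the outcome truly steps at nine, high/low is the right form and little is lost.

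**5. What it means for power, as an illustration.** Assume 60 participants (six listed groups at the minimum of 10) and a true correlation of 0.4 between score and outcome. Fisher's transformation gives power Φ[atanh(ρ)√57 − 1.96].

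| Form of literacy | ρ | Power |
|---|---|---|
| Score | 0.4 | 89% |
| 50:50 split | 0.4 × 0.798 = 0.319 | 70% |
| 80:20 split | 0.4 × 0.700 = 0.280 | 58% |

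**The case against.** The strongest reply is that little hangs on this. Technology varies within participant, so the choice of prototype compares each person with themselves and does not rest on the literacy factor. The SUS power statement stands. Literacy is only to add detail to a program theory that interviews and recordings also feed. The raw score is collected, so nothing is lost for good. All of this is right, and it limits how much weight the point should carry.

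The size of the loss is also conditional. The number-versus-graph pattern in the Background does not establish a straight-line effect, and neither the score distribution nor a total of 60 participants is given. This stands too, so the figures must carry their conditions.

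A reader might go further and infer several things that the Protocol does not support:

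- **That a third or more of the information is lost whatever the data.** A flat score loses about 31%, and a true step at nine loses little.
- **That fixing nine in advance is a fault.** Strata are needed before randomisation, when the median of these participants is not yet known. A preset cut is reasonable for that purpose.
- **That calling it a median split is a mistake.** It may be the median reported with the cited scale. That source is not at hand, so an error is not shown.
- **That the factor doubles the cells of a thin role-by-audit design, or leaves role comparisons confounded by literacy.** Role and audit are not evidently fully crossed, no full set of interactions is promised, no causal comparison of roles is a stated aim, and neither effect can be quantified from the Protocol.

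None of these replies argues for using two levels in the analysis when the score is already recorded.

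**Conclusion.** The point holds as a matter of efficiency. The Protocol reduces a collected 13-item score to two levels and analyses it only in that form, although learning about literacy is a stated use of the analysis. With a roughly bell-shaped score and a linear effect, at most about two thirds of the information on literacy and its interaction with technology is kept: 64% for a normal score at an even split, and 49% if 80% score high. The size rests on those two conditions, and on an assumed split wherever it departs from even. The conclusions on SUS and on which prototype to take forward do not depend on it. I class it as a cheap improvement.

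**What to change.** In section 2c, Analysis, state that graph literacy will enter as the 0-13 score, as a continuous between-participant covariate with a score-by-technology interaction. Linearity should be checked, for example with a squared term. Keep the cut of nine for stratifying the randomisation and for descriptive tables, where a step at nine would also show.

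The cost is a sentence of analysis wording and one extra check, with no added participants, data or burden. The price is reliance on linearity. The squared correlation works in both directions, so a straight line would capture only part of a true step at nine, and the check should therefore be reported with the result.

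### The user experiment does not list period as a factor and states no balancing of technology order, so any practice effect costs precision in the smaller comparisons of displays

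*Protocol*

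**What the plan says.** All of this is in the Protocol, Phase 2, section 2c (Controlled user experiment).

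- **Exposure.** "Each participant will complete a series of tasks in each condition". There are three conditions, so each person passes through three periods.
- **Factors.** The design has "technology (current presentation of NCA data and two QualDash prototypes) and task as within-participant variables". Between participants, it varies the user's role, which of the two audits is shown, and the level of graph literacy. Neither list contains period, position or order.
- **Order.** "The order of technology used and the task order will be determined by a computer randomisation program". No blocking or counterbalancing is described. Participants are stratified by graph literacy before randomisation, but the text does not say that orders are balanced within those strata.
- **Outcomes and analysis.** "The key outcome measure we will use is the overall system usability scale (SUS) score". Task time, accuracy, certainty and workload are analysed too, all by ANOVA, with no model terms written out.
- **Use of the result.** The Phase 2 summary of method and the 2c analysis paragraph both say that the experiment helps decide which prototype goes into the Phase 4 evaluation.

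**The concern.** People usually get quicker and surer as they repeat similar tasks. In a within-participant design that gain is tied to the position of a display. If the model has no term for position, the gain goes into the residual. If orders are drawn freely for a small group, one display may by chance fall later more often than another. With 10 people, for example, the split of which of two displays comes first is 7:3 or more uneven with probability 2 × 176/1024 = 34%.

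At stake is the precision with which displays are compared. The prototypes enter the experiment only after the focus groups have found both comprehensible, usable and acceptable. A gap as wide as 20 units between them is therefore unlikely, and the choice may rest on a smaller one.

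**Working it through.** **Inputs from the Protocol (2c, Sample).** "Given a standard deviation for SUS of 10 units"; target difference 20 units; at least 10 participants per group; three displays. **Assumed, because the Protocol gives no figure:** two-sided alpha 0.05; within-person correlation 0.5, so the within-person error variance is σ² = 50; a learning gain of b units per position, with b = 0, 3, 5 or 10.

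**1. The plan's own power.** For a two-sample t-test, the noncentrality is 20 / (10 × √(2/10)) = 4.47 on 18 df. Power is 98.8% for one comparison. With alpha divided by the number of comparisons it is 97.2% for two, 90.7% for seven and 89.7% for eight. The stated figures reproduce.

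**2. What learning adds to the error.** Over the six orders, the positions of two given displays differ by ±1 in four orders and by ±2 in two. The variance of the learning part of their within-person difference is (4b² + 2 × 4b²)/6 = 2b². The full variance is 2σ² + 2b², an inflation of 1 + b²/σ²:

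- b = 3: 1 + 9/50 = 1.18
- b = 5: 1 + 25/50 = 1.50
- b = 10: 1 + 100/50 = 3.00

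At N=10 the standard error is √((100 + 2b²)/10), which gives 3.2, 3.4, 3.9 and 5.5 for b = 0, 3, 5 and 10.

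**3. Chance imbalance of orders.** Its mean is zero and its SD is b√(2/N). At N=10 that is 1.3, 2.2 and 4.5 units for b = 3, 5 and 10. At N=60 it is 0.5, 0.9 and 1.8.

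**4. Simulation with freely drawn orders, N=10** (repeated-measures analysis of three displays, 18 error df without a period term and 16 with it).

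| b | SE without period | SE with period | Power at 20 units, without / with | Power at 5 units, without / with |
|---|---|---|---|---|
| 0 | 3.1 | 3.3 | 100% / 100% | 33% / 29% |
| 3 | 3.4 | 3.3 | 100% / 100% | 29% / 30% |
| 5 | 3.8 | 3.3 | 99.9% / 100% | 21% / 28% |
| 10 | 5.4 | 3.3 | 94% / 100% | 13% / 29% |

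The 5-unit difference is an illustration; the Protocol does not power for it. With no true difference, rejection rates are 0.048 to 0.051 without the term and 0.046 to 0.053 with it. At N=60 the standard errors are 1.3, 1.4, 1.6 and 2.2 without the term and 1.3 with it. Power for 5 units at b = 5 is then 87% without and 96% with.

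The Protocol clearly asks for SUS only after each prototype. For SUS the formula in step 2 still applies to the prototype difference, but with fewer error df than in the simulation.

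**5. Learning passed only between the prototypes.** Suppose using one prototype adds L to the other when that one is met later. Each prototype comes after the other in half the orders, so each gains L/2 on average and the current presentation gains nothing. Prototype versus prototype is unbiased. QualDash versus current shifts by L/2, or 1.5 to 5 units for an assumed L of 3 to 10.

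**The case against.** The strongest reply is that randomising the order is itself the safeguard. No display is systematically later, chance imbalance is ordinary sampling error that the ANOVA already counts, and type I error is correct. All of that stands. A reader might infer from the missing period term that later displays are favoured, or from the absence of a washout that the comparison is contaminated. The documents support neither. Order is random, and a pause would not undo learning.

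It also stands that the 20-unit target is safe, with power still 94% at 10 units of learning per position. Pooled over five or six user categories (about 50 to 60 people), chance imbalance is small. The choice of prototype also draws on interviews and recordings. Main effects of role and literacy are untouched, since everyone passes through all three periods.

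Finally, ANOVA model terms may properly be left to an analysis plan that is not shown, and nothing in 2c forbids a period term. That answers part of the point. Order balance is different: it must be fixed in the allocation list before data collection and cannot be restored afterwards.

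**Conclusion.** The point holds as a cheap improvement in precision; the Protocol contains no error here. Relative to a model with period, leaving it out raises the standard error at N=10 by about 2%, 15% and 64% for 3, 5 and 10 units of learning per position. The loss matters for comparisons of displays within a role group of about 10 and for prototype differences well under 20 units. The same mechanism applies to time, accuracy and workload, for which the Protocol gives no power statement.

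The size rests on the assumed learning gain and the within-person correlation of 0.5. With no learning nothing is lost by omitting period, and including it costs a little.

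A separate limit remains. Learning that passes only between the prototypes could favour QualDash over the current presentation on measures taken in all three conditions. A period term does not remove this.

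**What to change.** 1. Allocate the six technology orders in balanced blocks, within the literacy strata already planned and, where numbers allow, within role. Ten is not a multiple of six, so small role groups will be only nearly balanced.
2. Add period (1st, 2nd, 3rd) as a within-participant factor in the ANOVAs. The two changes belong together: with balanced orders but no period term, the residual would still carry the practice effect and the tests would be conservative.
3. Report first-period results, pooled over roles, as a descriptive check on learning between the prototypes. With 50 to 60 people that is about 17 to 20 per display. Within a role group of 10 it is about three, too few to use.

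**Cost.** A different allocation list, settled before the first participant, and two degrees of freedom. If there is no learning, the standard error at N=10 goes from about 3.1 to 3.3 under freely drawn orders. No extra participants, sessions or measures are needed.

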Phase 1: Interviews with members of clinical teams, quality sub-committees, and boards across five NHS acute Trusts and relevant commissioners will be used to articulate how NCA data are currently used (or not) in practice, identifying blockages to effective use and how these might be overcome. Interviews will consider a range of NCAs but will focus on the Myocardial Ischaemia National Audit Project (MINAP) and the Paediatric Intensive Care Audit Network (PICANet). Initial requirements for the design of QualDash derived from the interview data will be discussed at a workshop with suppliers of other NCAs to determine which requirements are generalisable to all NCAs.

Phase 2: QualDash will be developed through an iterative process, involving focus groups with clinical teams, quality sub-committee members, and board members from one Trust, relevant commissioners, and patients and carers. A controlled user experiment will assess comprehension, usability, and acceptability of QualDash prototypes, in comparison with existing formats for feedback of NCA data.

Phase 3: An implementation strategy for QualDash, tailored to the five Trusts and relevant Clinical Commissioning Groups (CCGs), will be developed through focus groups with clinical teams, quality sub-committees, and boards from the five Trusts and relevant commissioners. Planned implementation activities will be delivered across the five Trusts and with relevant commissioners.

Phase 4: QualDash will be made available in the five Trusts and relevant CCGs. A controlled interrupted time series (CITS) analysis will investigate impacts of QualDash, using process measures for MINAP and PICANet. Ethnographic observations and interviews over 12 months will provide insight into contexts and mechanisms that lead to those impacts. A questionnaire will be used to gather data on perceived usefulness of QualDash.

Phase 5: The feasibility of conducting a cluster randomised controlled trial (CRT) of QualDash will be assessed. If progression criteria are met, a CRT will be designed, using the CITS results to decide what effect size the trial should be powered to detect. Two focus groups will explore the suitability of QualDash for a range of other NCAs.

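### SUS, the key outcome of the user experiment, is scheduled only after the two prototypes, so the promised comparison with existing formats cannot be made on that scale

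*Protocol*

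**What the plan says.** The Summary of Research, under Phase 2, states the aim: "A controlled user experiment will assess comprehension, usability, and acceptability of QualDash prototypes, in comparison with existing formats for feedback of NCA data".

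Section 2c (Controlled user experiment), under Sample, names the outcome: "The key outcome measure we will use is the overall system usability scale (SUS) score". The power statement in that paragraph rests on SUS. Under Data collection the design is mixed factorial, with "technology (current presentation of NCA data and two QualDash prototypes) and task as within-participant variables"; role, audit and graph literacy vary between participants.

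The same Data collection text then sets the timing of SUS: "following completion of tasks on each prototype participants will be asked to complete the system usability scale (SUS". The purpose given in that sentence is to assess the QualDash prototypes. Decision, certainty and NASA task load are recorded after every task, task time is recorded, and tasks are done in every condition. Under Analysis, SUS is listed with time, accuracy, certainty and workload as data for analysis of variance.

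**The concern.** The experiment has a control condition, and the summary promises a usability and acceptability comparison against it. The one scale named for usability and acceptability is not given in that condition.

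This is a matter of data collection, so an analysis plan cannot repair it afterwards. If researchers follow the text, each participant completes SUS twice, not three times. On its key outcome the experiment could then rank the two prototypes but could not say whether either is better than the formats Trusts already have. That bears on Question C (the most effective means of viewing and interacting with audit data), which the Phase 2 summary of method says this experiment will help to answer.

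**Working it through.** **1. Does the word prototype cover the current presentation?** No. Section 2c lists the current presentation separately from the two prototypes when it defines the technology factor. Where the Data collection text means all three technologies, it speaks of conditions: tasks are done in each condition, and the closing interviews follow the tasks in all conditions. The SUS sentence uses the narrower word.

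**2. What is measured where, as written**

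| Measure | Current presentation | Prototype 1 | Prototype 2 |
|---|---|---|---|
| Time, accuracy, certainty, NASA workload | yes | yes | yes |
| SUS | not scheduled | yes | yes |
| Closing interview on views of the technology | not stated | yes | yes |

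**3. Technology contrasts on SUS.** Three levels give 3 × 2 / 2 = 3 pairwise contrasts. With SUS at two levels, 2 × 1 / 2 = 1 can be estimated (prototype 1 against prototype 2). Of the two contrasts with the current presentation, none can be.

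**4. The plan's own power figures.** Inputs from section 2c, Sample:
- Standard deviation of SUS: 10 units.
- Difference to be detected: 20 units.
- Group size and power for one comparison: "When there are at least 10 participants per group such a difference can be achieved with 98.8% power for a single comparison".
- Power stated for several comparisons: 97.2% for two, and above 90% for as many as seven.

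Two-sided alpha of 0.05 and a Bonferroni division by the number of comparisons m are my assumptions; the protocol states neither.

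Standardised difference d = 20 / 10 = 2. For two independent groups of n = 10, the degrees of freedom are 2n − 2 = 18 and the noncentrality is d × √(n/2) = 2 × √5 = 4.47. Power from the noncentral t distribution at alpha 0.05/m:

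| m | Computed | Stated |
|---|---|---|
| 1 | 98.82% | 98.8% |
| 2 | 97.17% | 97.2% |
| 7 | 90.68% | more than 90% |
| 8 | 89.66% | not stated |

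All stated figures reproduce. They do so as a comparison of independent groups.

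**5. Would the sample support all three contrasts if SUS were collected in every condition?** At alpha 0.05/3 the same independent-groups formula gives 95.6%. For a paired contrast with 10 participants, the degrees of freedom are 9 and the noncentrality is [d / √(2(1 − ρ))] × √10, where ρ is the within-person correlation of SUS scores. The protocol gives no ρ, so a range is shown:

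| Assumed ρ | Noncentrality | Power at 0.05/3 |
|---|---|---|
| 0 | 4.47 | 90.9% |
| 0.3 | 5.35 | 97.9% |
| 0.5 | 6.32 | 99.8% |

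On the protocol's own assumptions for SD and difference, the existing sample size is enough for all three contrasts.

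**The case against.** The strongest reply is that a prototype-only SUS is deliberate. The sentence that schedules it gives assessment of the prototypes as its purpose, and the closing interviews have the same scope. The decisions named for the experiment are which prototype goes to Phase 4 and what revisions it needs. SUS on both prototypes serves those decisions, and the bands in section 2c (below 50 poor, above 80 very good) allow an absolute reading. This stands as far as the choice of prototype goes. It does not remove the conflict with the summary, which promises usability and acceptability against existing formats, or explain why the key outcome omits one level of the factor under study.

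A second reply is that comparison with existing formats survives on other measures. That is correct: time, accuracy, certainty and workload are available in all conditions and bear on comprehension and effort. A reader might infer that no comparison with current formats is possible at all; the documents do not support that. What is missing is the comparison on SUS, and no other stated measure is directed at acceptability in the control condition.

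A third reply concerns power. A reader might infer that the experiment was powered for prototype against current presentation, so that the 98.8% has lost its control arm. The protocol does not say so. It speaks of participants per group, asks for at least 10 per group after listing the user categories, and its figures reproduce as an independent-groups test. That form fits user categories at least as well as a within-participant technology contrast. SUS comparisons between user groups on the prototypes remain possible. This reply stands in full.

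**Conclusion.** The inconsistency is real. The SUS schedule in section 2c does not match the comparison promised in the Phase 2 summary or the three-level technology factor. Its size is two of three technology contrasts on the key outcome, including every SUS contrast with the existing format.

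The conclusion rests on reading prototype as QualDash prototype, which is how the protocol uses the word. It does not depend on any power calculation: the stated figures are arithmetically sound under the assumed two-sided 0.05 and Bonferroni adjustment, and no error in them is claimed.

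This is a point that should be fixed, not one that threatens the study. The experiment is a formative part of Phase 2. SUS is not a Phase 4 outcome, does not enter the Phase 4 sample size, and is not among the Phase 5 progression criteria.

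**What to change.** In section 2c, Data collection, reword the SUS sentence along these lines: after finishing the tasks in each condition (the current presentation and both prototypes), every participant completes the SUS. Widen the purpose clause of that sentence so that it covers the comparison with the current presentation. Prototype against current presentation can then be estimated within participants.

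The cost is one more 10-item form per participant and a changed sentence. No new instrument is needed, since the protocol itself describes SUS as suited to any technology and quick to complete, and the planned sample need not grow.

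If a prototype-only SUS is what the investigators intend, leave section 2c as it is. Instead, narrow the Phase 2 summary so that the comparison with existing formats is claimed only for the measures taken in all three conditions. That costs one sentence, but gives up the SUS comparison with current practice.
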